### **8.2.5. COVID-19 Signs and Symptoms**

On Day 1, participants will complete the COVID-19 signs and symptoms ([Appendix 10](#)) in the study diary, before receiving study intervention. COVID-19-related symptoms will be evaluated in accordance with FDA guidelines. Participants will record a rating of their symptom severity over the past 24 hours based on a 4-point scale in which 0 is reported if no symptoms were present; 1 if mild; 2 if moderate; and 3 if severe.

Vomiting and diarrhea will each be rated on a 4-point frequency scale where 0 is reported for no occurrence, 1 for 1 to 2 times, 2 for 3 to 4 times, and 3 for 5 or greater.

Sense of smell and sense of taste will each be rated on a 3-point Likert scale where 0 is reported if the sense of smell/taste was the same as usual, 1 if the sense of smell/taste was less than usual, and 2 for no sense of smell/taste.

## **8.3. Safety Assessments**

Planned time points for all safety assessments are provided in the [SoA](#). Unscheduled safety measurements may be obtained at any time during the study to assess any perceived safety issues.

### **8.3.1. Targeted Physical Examinations**

Physical examinations to be completed before administration of study intervention.

A targeted physical examination will include, at a minimum, cardiopulmonary assessments. Investigators should pay special attention to any previously identified or new AE/targeted condition that the participant has experienced. Height and weight will also be measured and recorded at screening, though height may be self-reported for participants  $\geq 18$  years of age.

Investigators should pay special attention to clinical signs related to previous serious illnesses.

Physical examination findings collected during the study will be considered source data and will not be required to be reported, unless otherwise noted. Any untoward physical examination findings that are identified during the active collection period and meet the definition of an AE or SAE ([Appendix 3](#)) must be reported according to the processes in [Sections 8.4.1 to 8.4.3](#).

### **8.3.2. Vital Signs**

Any untoward vital sign findings that are identified during the active collection period and meet the definition of an AE or SAE ([Appendix 3](#)) must be reported according to the processes in [Sections 8.4.1 to 8.4.3](#).

Temperature, pulse rate, respiratory rate, oxygen saturation level, and blood pressure will be assessed as specified in the [SoA](#).

#### **8.3.2.1. Blood Pressure and Pulse Rate**

BP and PR measurements will be assessed with the participant, preferably in the supine or seated position with their feet on the floor when possible with a completely automated device. It is recommended that the same position should be used for a participant throughout the study duration. Manual techniques will be used only if an automated device is not available.

#### **8.3.2.2. Temperature and Respiratory Rate**

Temperature, and respiratory rate, will be assessed.

#### **8.3.2.3. Oxygen Saturation Level**

Oxygen saturation level will be assessed as part of the vital signs assessment.

#### **8.3.2.4. At-Home Devices for Vital Signs**

Each participant will also be supplied with a pulse oximeter to be used based on the instruction and medical judgment of the site investigator.

### **8.3.3. Point-of-Care Serum Creatinine Assessments**

A serum creatinine point-of-care device will be used to assess kidney function as described in the [SoA](#) and [Appendix 2](#).

### **8.3.4. Clinical Safety Laboratory Assessments**

Laboratory safety parameters will be graded according to the DAIDS Table for Grading the Severity of Adult and Pediatric Adverse Events, version 2.1. See [Appendix 2](#) for the list of clinical safety laboratory tests to be performed and the [SoA](#) for the timing and frequency. All protocol-required laboratory assessments, as defined in [Appendix 2](#), must be conducted in accordance with the laboratory manual and the [SoA](#). Unscheduled clinical laboratory measurements may be obtained at any time during the study to assess any perceived safety issues.

The investigator must review the laboratory report, document this review, and record any clinically significant changes occurring during the study in the AE section of the CRF. Clinically significant abnormal laboratory test findings are those that are not associated with the underlying disease, unless judged by the investigator to be more severe than expected for the participant's condition.

All laboratory tests with values considered clinically significant and abnormal during participation in the study or within 28 days after the last dose of study intervention should be repeated until the values return to normal or baseline or are no longer considered clinically significant by the investigator or study medical monitor.

If such values do not return to normal/baseline within a period of time judged reasonable by the investigator, the etiology should be identified and the sponsor notified.

See [Appendix 6](#) for suggested actions and follow-up assessments in the event of potential DILI.

See [Appendix 7](#) for instructions for laboratory testing to monitor kidney function and reporting laboratory test abnormalities.

#### **8.3.4.1. Alternative Facilities for Clinical Safety Laboratory Assessment**

If a local laboratory is used, qualified study site personnel must order, receive, and review results. Site staff must collect the local laboratory reference ranges and certifications/accreditations for filing at the site. Laboratory test results are to be provided to the site staff as soon as possible. The local laboratory reports should be filed in the participant's source documents/medical records. Relevant data from the local laboratory report should be recorded on the CRF.

#### **8.3.5. Pregnancy Testing**

A serum or urine pregnancy test is required at screening. Following screening, pregnancy tests may be urine or serum tests, and must have a sensitivity of at least 25 mIU/mL. Pregnancy tests will be performed in WOCBP at the times listed in the [SoA](#). Pregnancy tests will also be done whenever 1 menstrual cycle is missed during the active treatment period (or when potential pregnancy is otherwise suspected) and at Day 44 or ET visit. Pregnancy tests may also be repeated if requested by IRBs/ECs or if required by local regulations. If a urine test cannot be confirmed as negative (eg, an ambiguous result), a serum pregnancy test is required. In such cases, the participant must be excluded if the serum pregnancy result is positive.

For female pediatric participant who becomes pregnant, this information will be shared with the study participant's parent/guardian if the participant's age is within specific range based on local/country regulations.

##### **8.3.5.1. At-Home Pregnancy Testing**

A home urine pregnancy testing kit with a sensitivity of at least 25 mIU/mL may be used by the participant to perform the test at home, if compliant with local regulatory requirements. The pregnancy test outcome should be documented in the participant's source documents/medical records and relevant data recorded on the CRF. Confirm that the participant is adhering to the contraception method(s) required in the protocol.

#### **8.4. Adverse Events, Serious Adverse Events, and Other Safety Reporting**

The definitions of an AE and an SAE can be found in [Appendix 3](#).

AEs may arise from symptoms or other complaints reported to the investigator by the participant (or, when appropriate, by a caregiver, surrogate, or the participant's legally

authorized representative), or they may arise from clinical findings of the investigator or other healthcare providers (clinical signs, test results, etc).

The investigator and any qualified designees are responsible for detecting, documenting, and recording events that meet the definition of an AE or SAE and remain responsible to pursue and obtain adequate information both to determine the outcome and to assess whether the event meets the criteria for classification as an SAE or caused the participant to discontinue the study intervention (see [Section 7.1](#)).

During the active collection period as described in Section 8.4.1, each participant/parent/legal guardian/legally authorized representative will be questioned about the occurrence of AEs in a nonleading manner.

In addition, the investigator may be requested by Pfizer Safety to obtain specific follow-up information in an expedited fashion.

#### **8.4.1. Time Period and Frequency for Collecting AE and SAE Information**

The time period for actively eliciting and collecting AEs and SAEs (“active collection period”) for each participant begins from the time the participant provides informed consent, which is obtained before undergoing any study-related procedure and/or receiving study intervention, through and including a minimum of 28 calendar days, except as indicated below, after the last administration of the study intervention.

Follow-up by the investigator continues throughout the active collection period and until the AE or SAE or its sequelae resolve or stabilize at a level acceptable to the investigator.

When a clinically important AE remains ongoing at the end of the active collection period, follow-up by the investigator continues until the AE or SAE or its sequelae resolve or stabilize at a level acceptable to the investigator and Pfizer concurs with that assessment.

For participants who are screen failures, the active collection period ends when screen failure status is determined.

If the participant withdraws from the study and also withdraws consent for the collection of future information, the active collection period ends when consent is withdrawn.

If a participant permanently discontinues or temporarily discontinues study intervention because of an AE or SAE, the AE or SAE must be recorded on the CRF and the SAE reported using the PSSA.

After the defined active collection period for safety events, long-term follow-up visits are also conducted at Weeks 12 and 24. Any new SAE occurring during this long-term follow-up period and determined to be related to study intervention must be reported to Pfizer Safety immediately upon awareness and under no circumstance should this exceed 24 hours.

Investigators are not obligated to actively seek information on AEs or SAEs after the participant has concluded study participation. However, if the investigator learns of any SAE,

including a death, at any time after a participant has completed the study, and they consider the event to be reasonably related to the study intervention, the investigator must promptly report the SAE to Pfizer using the PSSA.

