**Table 1. Study Schedule of Assessment**

Visit Identifier Abbreviations used in this table may be found in Section 10.11 .	Screening	Baseline (Day 1)	Day 5	Day 10	Day 15	Day 21	Day 28	Day 35	Day 44	LTF/U		ET (plol' to Day 44)	Notes
										Week 12	Week 24		
Visit Window	Day-1 to Day 1	0 days	±1 day	±1 day	±2 days	±2 days	±2 days	±3 days	±3 days	±7 days	±7 days	±5 days	
 
Screening procedures may be done from Day -1 to Day 1, and may be completed on the same calendar day as Baseline/Day 1 procedures. If screening and baseline visits are conducted on the same calendar day, assessments and procedures that are listed to occur at both visits only need to be completed once.
 

Study Visit Location	S	S	S	S	SIP	
 
All study visits are expected to be in-person visits. Site staff should, in discussion with participants, determine the most appropriate location to conduct study visits. Visits should take place at the investigational site (S). If this is not feasible, then alternate venues may include the participant's location (P). Refer to Section 8.1.2 and Section 8.1.3.
 
If an in-person visit is held at a location other than the investigational site, the HCP performing the visit should perform all assessments. If the HCP is unable to collect all required information for the study visit (eg, AEs, concomitant medications, contraception), the site should contact the participant via a follow-up telephone call to collect the additional information possible. Refer to Section 8.1.4.
 
							
ELIGIBILITY													
Informed consent (and assent if applicable)	X												
 
Informed consent/assent should be obtained prior to undergoing any study-specific procedures.
 

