**Table 1. Study Schedule of Assessment**

Visit Identifier' Abbreviations used in this table may be found in Section 10.11.	Screening	Baseline (Day 1)	Day 5	Day 10	Day 15	Day 21	Day 28	Day 35	Day 44	LTF/U		ET (pilot to Day 44)	Notes
										Week 12	Week 24		
Visit Window	Day -1 to Day 1	0 days	bl:1 day	bl:1 day	±2 days	±2 days	±2 days	±3 days	±3 days	±1 days	±7 days	±5 days	
 
Screening procedures may be done from Day -1 to Day 1, and may be completed on the same calendar day as Baseline/Day 1 procedures. If screening and baseline visits are conducted on the same calendar day, assessments and procedures that are listed to occur at both visits only need to be completed once.
 

Study intervention dispensation		X	X	X									
 
Study intervention will be dispensed on Day 1, Day 5, and Day 10 (see Section 6.1.1).
 
Should eGFR or eCrCl (based on the point-of-care creatinine) on Day 5 or Day 10 warrant a dose modification, replacement study intervention will be dispensed on Day 5 or Day 10. See Section 10.7.1 for age specific kidney function calculations.
 
See Section 6.6.
 

Study intervention administration		Day 1 through Day 15											
 
Baseline assessments should be performed before administration of the first study intervention, except for PK sampling.
 
The first dose of study intervention will be administered to all participants on Day 1 during the in person visit. All subsequent doses of study intervention (ie, 29) will be self-administered (or administered to the participant by a legal guardian or caregiver). If only 1 dose of study intervention is administered on Day 1, study intervention administration should end on Day 16.
 
See Section 6.1.1.
 

Study Intervention Accountability													
Retrieval of unused study intervention and empty study intervention containers			X	X	X							X	
 
If the Day 15 visit is conducted prior to last dose of study intervention, empty study intervention containers and unused study intervention should be returned at the Day 21 visit.
 
See Section 6.5.
 

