**Table 1. Study Schedule of Assessment**

Visit Identifier Abbreviations used in this table may be found in Section 10.11.	Screening	Baseline (Day 1)	Day 5	Day 10	Day 15	Day 21	Day 28	Day 35	Day 44	LTF/U		ET (pilot to Day 44)	Notes
										Week 12	Week 24		
Visit Window	Day -1 to Day 1	0 days	±1 day	±1 day	±2 days	±2 days	±2 days	±3 days	±3 days	±1 days	±7 days	±5 days	
 
Screening procedures may be done from Day -1 to Day 1, and may be completed on the same calendar day as Baseline/Day 1 procedures. If screening and baseline visits are conducted on the same calendar day, assessments and procedures that are listed to occur at both visits only need to be completed once.
 

													
 
After the defined active collection period for safety events, long-term follow-up visits are also conducted at Weeks 12 and 24. Any new SAE occurring during this long-term follow-up period and determined to be related to study intervention must be reported to Pfizer Safety immediately upon awareness and under no circumstances should this exceed 24 hours.
 
See Section 8.4.3 for follow-up AE and SAE assessments.
 

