The total study duration is up to 24 weeks, including study intervention administration through Day 15 or Day 16, safety assessments through Day 44, efficacy assessments through Week 24, and long-term follow-up at Weeks 12 and 24.

Analyses will be conducted after the main study population is fully enrolled and have completed the Day 44 visit regardless of the number of randomized participants in the population with rebound. There will be 2 analysis time points for reporting the results of this study. The primary analysis will be performed after all participants in the main study population have completed the Day 44 visit. The follow-up analysis will be performed after all participants in the main study population have completed the Week 24 visit. In addition, both analyses (primary and follow-up) will include separate results for the main study population and the additional population with rebound.

An independent E-DMC will review unblinded data to ensure the safety of participants on an ongoing basis throughout the duration of the study (Section 10.1.5.1).

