## **6. STUDY INTERVENTION(S) AND CONCOMITANT THERAPY**

Study interventions are all prespecified investigational and noninvestigational medicinal products/auxiliary medicinal products, medical devices, and other interventions (eg, surgical and behavioral) intended to be administered to the study participants during the study conduct.

For the purposes of this protocol, study intervention refers to nirmatrelvir 150 mg tablets and matching placebo and ritonavir 100 mg capsules and matching placebo.

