### **10.4.2. Female Participant Reproductive Inclusion Criteria**

The criteria below are part of Inclusion Criterion 1 (Age and Sex; [Section 5.1](#)) and specify the reproductive requirements for including female participants. Refer to [Section 10.4.4](#) for a complete list of contraceptive methods permitted in the study.

- A female participant is eligible to participate if at least 1 of the following conditions applies:
  - Is not a WOCBP (see definition in Section 10.4.3).
    - OR
  - Is a WOCBP who is pregnant (at least 14 weeks gestation).
    - OR
  - Is a WOCBP who is not pregnant at screening and agrees to use a highly effective contraceptive method (failure rate of  $< 1\%$  per year) during the intervention period and for at least 28 days after the last dose of study intervention, which corresponds to the time needed to eliminate any reproductive safety risk of the study intervention(s). If a highly effective, user-dependent method is chosen, she agrees to concurrently use an effective barrier method of contraception. The investigator should evaluate the effectiveness of the contraceptive method in relationship to the first dose of study intervention.

The investigator is responsible for review of medical history, menstrual history, and recent sexual activity to decrease the risk for inclusion of a woman with an early undetected pregnancy.

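### The ±3-day window on the Day 44 visit means the Schedule of Activities does not guarantee the 28-day minimum AE/SAE collection in Protocol 8.4.1

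*Protocol*

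**What the plan says.** Protocol 8.4.1 starts active collection of AEs and SAEs at informed consent and continues it "through and including a minimum of 28 calendar days, except as indicated below, after the last administration of the study intervention". The exceptions that follow are screen failure and withdrawal of consent; for the latter, "the active collection period ends when consent is withdrawn". An early visit is not an exception.

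Section 4.1 gives the timeline as "including study intervention administration through Day 15 or Day 16, safety assessments through Day 44". Table 1 explains the later dosing day: "If only 1 dose of study intervention is administered on Day 1, study intervention administration should end on Day 16". Section 6 counts placebo as study intervention ("study intervention refers to nirmatrelvir 150 mg tablets and matching placebo and ritonavir 100 mg capsules and matching placebo"), so the last administration falls on Day 15 or 16 in all three arms when the course is completed.

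In Table 1 the AE-monitoring row is marked from screening to Day 44 and at early termination, and is blank at Weeks 12 and 24. The Day 44 visit has a window of ±3 days. For the period after active collection, the note to that row limits reporting to this: "Any new SAE occurring during this long-term follow-up period and determined to be related to study intervention".

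**The concern.** Section 8.4.1 sets a minimum in days since the last dose. The schedule that sites follow sets a visit with a symmetric window. Nominal Day 44 leaves almost no slack over that minimum, so a visit held a few days early can be in window and still come before the minimum is reached.

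A site could then keep every visit in window, record no visit deviation, and hold no scheduled contact that asks about the last days of the required period. Incidence of TEAEs and of SAEs are secondary endpoints, and 8.4.1.2 requires every AE in the active period to be recorded. What is at stake is the completeness of those counts over the last few days, mainly for nonserious AEs and for SAEs unrelated to study intervention.

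**Working it through.** **Inputs**

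- Minimum collection after the last administration: 28 days (Protocol 8.4.1).
- Last dose: Day 15, or Day 16 if only one dose was taken on Day 1 (4.1 and Table 1). Placebo counts (Section 6).
- Day 1 is the start of study intervention (Table 1).
- Last visit with AE monitoring: Day 44 ±3 days, so Day 41 to Day 47 (Table 1).
- Next scheduled visit: Week 12 ±7 days, with the AE row blank (Table 1). Its earliest day is 84 − 7 = Day 77.

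**Formulas**

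- Gap = visit day − day of last dose.
- Shortfall = 28 − gap if that is positive, otherwise 0.
- Earliest visit day that meets the minimum = day of last dose + 28.

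**Nominal schedule first.** 44 − 15 = 29 and 44 − 16 = 28. The minimum is met on nominal Day 44, with 1 or 0 days to spare.

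**Each permitted visit day**

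| Visit day | Gap, last dose Day 15 | Shortfall | Gap, last dose Day 16 | Shortfall |
|---|---|---|---|---|
| 41 | 26 | 2 | 25 | 3 |
| 42 | 27 | 1 | 26 | 2 |
| 43 | 28 | 0 | 27 | 1 |
| 44 | 29 | 0 | 28 | 0 |
| 45 to 47 | 30 to 32 | 0 | 29 to 31 | 0 |

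**Earliest day that meets the minimum.** 15 + 28 = Day 43 and 16 + 28 = Day 44. The early side of the window could therefore be 1 day or 0 days, against the 3 days allowed.

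**Who is affected.** 41 − 28 = 13, so a participant whose last dose was on Day 13 or earlier has at least 28 days even at a Day 41 visit. The gap concerns last doses on Day 14 or later (41 − 14 = 27, one day short) combined with an early visit.

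**What comes next.** After a Day 41 visit the next scheduled visit is no earlier than Day 77, which is 36 days later, and AE monitoring is not marked there.

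**The case against.** The strongest reply is that the two texts can both be obeyed. Section 8.4.1 defines the period by days since the last dose, so a Day 41 visit does not close it. Sections 8.4.1.1 and 8.4.1.2 still require SAEs to be reported and AEs to be recorded whenever they occur in that period. Section 1.3 allows unplanned visits, and 8.1.4 allows telehealth. Week 12 also collects vital status, COVID-19 signs and symptoms, and COVID-19-related medical visits since the last assessment, so deaths and COVID-19 hospitalizations in the gap would surface.

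This stands in part. It rules out the reading that the schedule and 8.4.1 flatly contradict each other, since nominal Day 44 complies. It also rules out the reading that unrelated SAEs stop being reportable once an early visit is over: that limit applies to events after the active period, so an unrelated SAE on Day 42 is still reportable if it becomes known. What remains is elicitation. Telehealth is offered when an in-person visit cannot be done, and nothing triggers it after an early visit that was completed.

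A reader might go further in three ways that the documents do not support.

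- **Other safety rows.** Section 10.4.2 asks participants to agree to contraception "for at least 28 days after the last dose of study intervention". That governs use and does not require a check or test on or after that day. The pregnancy test is set at Day 44 or early termination, and concomitant therapy is collected to the Day 44 visit; neither is tied to a 28-day minimum. These rows do not conflict with 10.4.2.
- **Arm imbalance.** Counted from the last active dose on Day 5, 10 or 15, a Day 41 visit gives 36, 31 and 26 days, and Day 44 gives 39, 34 and 29. The ordering and the 5-day steps are the same, so they come from the blinded common calendar and not from the window. The rule in 8.4.1 counts placebo and treats the arms alike.
- **Share affected.** The documents give no distribution of visit days within the window and no share of participants with a Day 16 last dose. Any percentage would be an assumption; the possible range is 0% to 100%.

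**Conclusion.** The Schedule of Activities does not guarantee the 28-day minimum in 8.4.1. For participants who complete dosing and stay in the study, an in-window last AE visit can fall 25 to 27 days after the last dose. The shortfall is at most 3 of 28 days (3/28, about 11%), comes only from the early side of the window, and is absent from nominal Day 44 onward.

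This is a small gap in completeness in a descriptive safety analysis. It is not evidence of bias between arms, and it does not touch the primary endpoint. It merits correction because a stated safety minimum can be missed by following the schedule exactly.

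The result assumes that the 28 days are counted from the day after the last dose. The protocol's own timeline fits that count, since 16 + 28 = 44. It also takes the table entries as read: AE monitoring blank at Weeks 12 and 24, and a ±3-day window at Day 44.

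**What to change.** Reconcile the AE-monitoring row, and the early side of its Day 44 window, with the 28-day minimum in 8.4.1, so that the last scheduled AE/SAE elicitation cannot come before the end of the active collection period. A note to that row in the Schedule of Activities is enough. It should state what happens when the Day 44 visit is held before 28 days have passed since the last dose.

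The cost is that note and at most a brief telehealth contact, a format the protocol already uses, for participants seen early. The Day 44 swab window stays as it is, and the contraception, pregnancy-test and concomitant-therapy rows need no change on this ground.
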